6.9 Efficacy Analysis

For exploratory efficacy analyses, descriptive statistics that are appropriate for the efficacy variable will be shown within each age group and treatment group (Group 1), type of surgery (Group 2), for the safety population.

6.9.1 Pain Intensity Score

Summary statistics will be presented for pain intensity scores at each assessment timepoint. These summaries will be based on the observed values at the scheduled time points. Data listings of pain intensity scores will also be provided.

Time windows will be derived for each post baseline visit using the time intervals for the study time windows detailed in Table 7.

Study Time	Time Interval for Study Time Window
Baseline	≥ 0 minutes prior to dose
Post-dose 4 hours	3.75 – 4.25 hours after end of study drug administration
Post-dose 8 hours	7.5 - 8.5 hours after end of study drug administration
Post-dose 12 hours	11 – 13 hours after end of study drug administration
Post-dose 24 hours	23 - 25 hours after end of study drug administration
Post-dose 36 hours	34 - 38 hours after end of study drug administration
Post-dose 48 hours	46 - 50 hours after end of study drug administration
Post-dose 60 hours	58 - 62 hours after end of study drug administration
Post-dose 72 hours	70 – 74 hours after end of study drug administration
Post-dose 96 hours	92 - 100 hours after end of study drug administration

 Table 7
 Analysis Study Time Windows for Pain Intensity Scores

If there are multiple pain intensity score values for the same parameter prior to the end of study drug administration, the last value will be chosen for Baseline. If there are multiple pain intensity score values in a post-end of study drug administration window, the value closest to the target time point will be chosen for analysis. Unscheduled visits can be mapped to a study time only if the scheduled assessment for that time was not done and an unscheduled visit falls into the time interval for the visit window. Data from both scheduled and unscheduled visits will be listed.

6.9.1.1 Area under the Curve

Area under the pain-time curve (AUC) is derived using the linear trapezoidal rule (see formula below) on the pain scores. AUC will start with the first pain assessment obtained after surgery and use all following pain assessments including those collected prior to administration of opioid medication and unscheduled assessments. Actual assessment times will be used in deriving AUC.

$$AUC = \left[\sum_{i=4}^{n} (p_i + p_{(i-1)})(t_i - t_{(i-1)})\right]/2$$

Where p_i is the pain intensity score at time *i*, and t_i is the time, in hours, from end of surgery. Note that *i* starts at 4 as this represents the first measurement post-surgery.

Summary statistics will be presented for the following pain intensity AUCs: AUC_{Adjusted(4-24)}, AUC_{Adjusted(4-24}

6.9.2 Opioid Consumption

Opioid medications will be converted to oral morphine equivalent dose (MED mg) using the appropriate conversion factor from Table 8 for all summaries. Opioids are collected on the Post Surgical Pain Medication and Prior/Concomitant Medications eCRF pages. The amount of total opioid dose will be calculated as the sum of the oral morphine equivalent of all opioids taken after surgery up to the timepoint of interest. Subjects with no opioid use during the period in question will be assigned a dose of 0 for summaries and changed to the lesser of 0.1 or half of the smallest total amount observed in the study, whichever is smaller, prior to being transformed with the natural logarithm for analysis. Total postsurgical opioid dose will be calculated through 24, 48, and 72 hours. In addition to the descriptive statistics for continuous data, geometric mean (GM) and coefficient of variation (CV) will also be included and mean and SD will be excluded.

For the calculation of the total dose through 72 hours, if a subject's last follow-up time is 72-x hours, then the approach described in Section 6.1.1.2 is used.

Medication	Unit	Route	Oral Morphine Conversion Multiplication Factor
Morphine, Morphine Sulfate	mg	IV,IM,SC	3
Morphine	mg	РО	1
Morphine	mg	R	1
Buprenorphine	mcg	IM	75
Buprenorphine	mcg	SL	37.5
Codeine (Tylenol 3, acetaminophen-coedine,	mg	РО	0.15
Paracetamol Forte, Tylenol 4,)			
Codeine Phosphate	mg	IM	0.24
Demerol, Meperidine, Pethidine	mg	IV,SC	0.3
Demerol, Meperidine, Pethidine	mg	РО	0.1
Fentanyl, Remifentanil	mcg	IV,PO,IM,TD	300
Hydromorphone	mg	R	4
Hydromorphone (Dilaudid)	mg	IV,IM,SC	20
Hydromorphone (Dilaudid)	mg	РО	4
Hydromorphone (Dilaudid)	mg	EP	45
Ketobemidone, Oxycodone	mg	IV	3
Methadone	mg	IM	3
Methadone	mg	РО	1.5
Methadone	mg	IV	6
Nalbuphine/Nallouphine (Nubain/Manfine)	mg	IV,IM,SC	3
Oxycodone, Oxycocet, Percocet, acetaminophen-	mg	PO	1.5
oxycodone, Oxycodone HCl			
Oxymorphone	mg	РО	3
Oxymorphone	mg	IM,SC	30
Pentazocine/Acetaminophen	mg	РО	0.2
Pentazocine/Naloxone	mg	PO	0.2

Table 8 Oral Morphine Equivalents

Pentazocine	mg	IM	1
Tapentadol	mg	PO	0.3
Ultram, Tramadol, Tramacol hydrochloride	mg	PO,IM	0.25
Vicodin, Norco, Lorcet, Lortab, hydrocodone-	mg	PO	1
acetaminophen, Ketobemidone			

Key: EP = Epidural; IM = Intramuscular; IV = Intravenous; INS = Intra Nasal Spray; NA = Not Applicable; PO = Oral; R = Rectal; SC = Subcutaneous; SL = Sublingual; TBD = To Be Determined; TD = Transdermal

If other rescue medications are given, then the conversion to oral Morphine Equivalent will be determined post-hoc. If a combination opioid product is given, then the oral Morphine Equivalent will be determined by the opioid part of the medication. Opioids given post surgically with an indication such as 'anesthesia maintenance' will not be included.

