12.6. Other Endpoints

Analysis of these other endpoints will be conducted for exploratory purposes only. The efficacy endpoints listed below will be assessed based on the efficacy measurements conducted at the time points specified.

- Pain intensity scores
- The AUC of pain intensity scores

- Total opioid consumption in morphine equivalents
- Time to first postsurgical use of opioid medication.

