6.5 Intraoperative, Prior, and Concomitant Medications

Intraoperative, Prior, and concomitant medications will be coded using the World Health Organization Drug Dictionary (WHO-DD) and will be classified according to the default anatomical therapeutic chemical (ATC 4) classification term and preferred term (PT).

Intraoperative medications are medications collected on Intraoperative Medication eCRF page. Intraoperative medications are defined as medications given as part of the surgical procedure. These may include anesthesia, opioids or other medications with start and stop dates on the day of surgery and start times overlapping within the surgery start and stop times.

Prior medications are defined as medications with a stop date and time prior to the start of surgery. Prior medications are recorded on the prior/concomitant medication eCRF page.

Concomitant medications are defined as medications taken after the start of study drug administration (i.e., started prior to the start of study drug administration and continued after or started after the start of study drug administration) and recorded on the prior/concomitant or post surgical pain medication CRF page.

Intraoperative, prior and concomitant medications will be summarized separately using the number and percentage of subjects within each age group and treatment group of the study by ATC class and PT for the safety population. Subjects may have more than one medication per ATC category and PT. At each level of subject summarization, a subject will be counted once if one or more medications are reported by the subject at that level.

A data listing will be created for all medications, with a flag variable identifying intraoperative, prior, and concomitant medications.

A listing mapping the ATC class and PT to verbatim term will be presented.

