Source: list SAS datasets used to create table

ddmmmyyyyThh:mm

SAS X.Y

program_name

Note to programmer: Other timepoints for this table are: 12 hours, 24 hours, 36 hours, 48 hours, 60 hours, 72 hours, 96 hours, and Hospital Discharge. Use this template also for tables:

Table 14.2-1.1.2: Summary of Color Analog Scale Pain Intensity Scores (Group 2: 6 to < 12 years) - Safety Population

Note to programmer: Replace treatment columns by Spine Surgery and Cardiac Surgery for this table.

Pacira Pharmaceutica	als (Page X of Y)	Pro	tocol: 402-C-319
Table 14.2-2.1.1: Su	ammary of AUC of Pain Intensity Scores (Group 1: 12 to <17	years) – Safet	y Population
Parameter	Statistic	EXPAREL 4 mg/kg [N=xx]	Bupivacaine HCl 2 mg/kg [N=xx]
AUC(4-24)	N Mean SD Median Minimum Maximum	xx xxx.x xxx.xx xxx.x xx xx xx	xx xxx.x xxx.xx xxx.x xx xx xx

AUC = area under the curve calculated using the trapezoidal method;

Source: list SAS datasets used to create table

SAS X.Y

 ${\tt ddmmmyyyyThh:}{\tt mm}$

program_name

Note to programmer: Other parameters to include in this table: AUC(4-48), AUC(4-72), AUC(4-96) and AUC(4-Hospital Discharge). Use this template also for:

Table 14.2-2.1.2: Summary of AUC of Pain Intensity Scores (Group 2: 6 to < 12 years) - Safety Population **Note to programmer:** Replace treatment columns by Spine Surgery and Cardiac Surgery for this table.

(Page X of Y)

Protocol: 402-C-319

Table 14.2-3.1.1: Summary of Total Opioid Consumption (MED mg) (Group 1: 12 to <17 years) - Safety Population

		EXPAREL	Bupivacaine HCl
		4 mg/kg	2 mg/kg
Time Period [1]	Statistic	[N=xx]	[N=xx]
0-24 hrs	n	XX	XX
	Geometric Mean	XX.X	XX.X
	%CV	X . XX	X.XX
	Minimum	XX	XX
	Median	XX.X	XX.X
	Maximum	XX	XX
0-48 hrs	n	XX	XX
	Geometric Mean	XX.X	XX.X
	%CV	X.XX	X.XX
	Minimum	XX	XX
	Median	XX.X	XX.X
	Maximum	XX	XX
0-72 hrs	n	XX	XX
	Geometric Mean	XX.X	XX.X
	%CV	x.xx	X.XX
	Minimum	XX	XX
	Median	XX.X	XX.X
	Maximum	XX	XX

[1] Time 0 is defined as the time of the end of surgery.

Source: list SAS datasets used to create table

SAS X.Y

ddmmmyyyyThh:mm

program name

Table 14.2-3.1.2: Summary of Total Opioid Consumption (MED mg) (Group 2: 6 to < 12 years) - Safety Population

Note to programmer: Use preceding Table as template. Replace treatment columns by Spine Surgery and Cardiac Surgery for this table.

(Page X of Y)

Protocol: 402-C-319

Table 14.2-4.1.1: Analysis of Time to First Postsurgical Opioid Medication Use (Group 1: 12 to <17 years) - Safety Population

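### SAP Table 8 applies multiplication factors of 300, 75 and 37.5 to microgram doses to obtain milligrams of oral morphine, so followed as written it overstates fentanyl, remifentanil and buprenorphine doses, apparently 1000-fold

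*SAP*

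**What the plan says.** SAP 6.9.2 expresses all opioid summaries as oral morphine equivalent dose in mg (MED mg). Table 8 gives a drug, a unit, a route and a multiplication factor for each row. A subject's total is the sum of converted doses after surgery, reported through 24, 48 and 72 hours.

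Three rows carry mcg: "Fentanyl, Remifentanil mcg IV,PO,IM,TD 300", "Buprenorphine mcg IM 75", and a sublingual buprenorphine row with factor 37.5. Every other row carries mg, including "Morphine, Morphine Sulfate mg IV,IM,SC 3".

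No mcg-to-mg step appears in 6.9.2, in the key to Table 8, in the text after the table, or in 6.1.1.2 on postsurgical opioids. The shell for Listing 16.2-7.2.1.1 shows dose with units, conversion factor and MED mg, with no column for a unit conversion.

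On which records count, the SAP says "Opioids are collected on the Post Surgical Pain Medication and Prior/Concomitant Medications eCRF pages". Two statements limit the reach: "Opioids given post surgically with an indication such as 'anesthesia maintenance' will not be included" (6.9.2) and "Intraoperative medications are medications collected on Intraoperative Medication eCRF page" (6.5).

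The results go into "Table 14.2-3.1.1: Summary of Total Opioid Consumption (MED mg) (Group 1: 12 to <17 years) - Safety Population" and its Group 2 counterpart, which show geometric mean, %CV, minimum, median and maximum. Protocol 12.6 says of this endpoint and its companions: "Analysis of these other endpoints will be conducted for exploratory purposes only".

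**The concern.** A factor that turns a dose into milligrams of oral morphine must match the unit of that dose. Factors of 300, 75 and 37.5 are of a size one would expect per milligram of these drugs, yet the table attaches them to micrograms. Followed as written, a single postsurgical fentanyl bolus would swamp everything else the subject received.

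Total opioid consumption is a named protocol endpoint, and the Group 1 table sets the EXPAREL and bupivacaine HCl columns side by side. If fentanyl, remifentanil or buprenorphine were used unequally between the arms, or between spine and cardiac surgery in Group 2, the unit slip would appear as a difference in opioid use. Postsurgical analgesia follows each institution's standard of care, so nothing in the plan rules these drugs out, and listing them in Table 8 shows that they are anticipated.

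**Working it through.** The plan gives no worked conversion, so there is no figure to reproduce.

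**Inputs from the documents.** Factors: 300 (fentanyl, remifentanil), 75 (buprenorphine IM) and 37.5 (buprenorphine SL), all with unit mcg; 3 for IV morphine in mg (SAP Table 8). Planned Group 1 arm size: 15 in each part, so 30 over both parts (SAP section 3).

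**Inputs assumed.** Illustrative doses, other-opioid background and number of affected subjects. The documents give none of these.

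**Step 1: one dose.** As written, MED = mcg × factor. With a unit step, MED = (mcg / 1000) × factor.

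| Dose | As written (mg) | With unit step (mg) |
|---|---|---|
| Fentanyl 100 mcg | 100 × 300 = 30,000 | 0.1 × 300 = 30 |
| Buprenorphine IM 300 mcg | 300 × 75 = 22,500 | 0.3 × 75 = 22.5 |
| Buprenorphine SL 300 mcg | 300 × 37.5 = 11,250 | 0.3 × 37.5 = 11.25 |

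**Step 2: plausibility against the documents.** As written, 1 mcg of fentanyl is 300 mg of oral morphine, or 300 / 3 = 100 mg of IV morphine by the table's own row. Protocol 7.4 reports 0–48 h geometric mean totals of 16.7 and 84.0 mg, in oral morphine equivalents, in an adult knee study. One microgram would exceed either total.

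**Step 3: one subject.** Assume 60 mg from other opioids plus 50 mcg of fentanyl. As written: 60 + 50 × 300 = 15,060 mg. With the unit step: 60 + 0.05 × 300 = 75 mg. The ratio is 15,060 / 75 = 200.8.

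**Step 4: geometric mean of an arm of 30.** With k such subjects, the inflation is 200.8^(k/30).

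| k | 0 | 1 | 3 | 5 | 10 |
|---|---|---|---|---|---|
| Inflation | 1.00 | 1.19 | 1.70 | 2.42 | 5.86 |

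Varying the background over 30, 60 and 100 mg and the fentanyl dose over 25, 50 and 100 mcg gives 1.15 to 1.23 for k = 1 and 2.03 to 2.82 for k = 5.

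**Step 5: other statistics in the table.**
- *Maximum.* With every background at 60 mg, one affected subject moves it from 75 to 15,060 mg.
- *Median.* With every background at 60 mg, it stays at 60 mg for up to 14 affected. With a lognormal background (assumed median 60 mg, log-SD 0.5 to 1.0; 20,000 simulated arms; median of the per-arm ratios), it moves 1.00-fold for k = 1, 1.07- to 1.20-fold for k = 5, and 1.27- to about 1.75-fold for k = 10.
- *%CV.* In the same simulation, at k = 5 and log-SD 0.5, the arithmetic CV goes from about 49% to 221%. The geometric CV goes from about 52% to 990%. The mock-up prints %CV under the geometric mean without saying which is meant.

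**The case against.** **The 1000-fold size is inferred.** Table 8 cites no source, and its morphine rows fix the scale only for morphine. This stands: the documents do not prove that the factors are mg-for-mg. What they do show is that the literal reading is untenable, by the comparison with the adult totals in Protocol 7.4. A stray extraction error is also unlikely, since three separate rows show the same pattern.

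**The harm arises only if the table is programmed literally.** A programmer may convert silently, and the listing prints dose, factor and MED side by side, so a maximum of 15,060 mg would be conspicuous. This is fair, but the plan instructs multiplication of the listed unit and specifies no check. A SAP should not depend on someone departing from it.

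**The summary-level figures are scenarios.** The background, dose and number affected are all assumed, and zero affected is as compatible with the documents as ten. This stands. The per-dose error does not depend on these assumptions; the effect on the tables does. The scenarios are for a Group 1 arm of 30. The Group 2 columns, split by surgery type, have no planned size and are not quantified.

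**The reach is narrow.** The endpoint is exploratory and carries no p-value. Intraoperative drugs have their own eCRF page, and anesthesia-maintenance opioids are excluded. The log-rank comparison planned for time to first opioid does not use Table 8, nor do PK, safety or pain scores. All of this is correct and limits the seriousness of the point without removing the error.

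**Conclusion.** The concern holds. Table 8 as written gives wrong oral morphine equivalents for fentanyl, remifentanil and buprenorphine, by a factor of 1000 per dose if the factors are mg-for-mg. That reading is an inference for the sponsor to confirm.

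In Table 14.2-3.1.1 the maximum, the geometric mean and the %CV are exposed, and the median much less so. How far they move depends on how many subjects have an included postsurgical record of these drugs. With none, nothing changes; with a few in an arm of 30, the geometric mean can be off by anything from about a fifth to well over double. The study's PK and safety objectives are unaffected. This should be fixed before the analysis is programmed, but it does not threaten the study's main conclusions.

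**What to change.** Ask the sponsor to confirm the source and basis of the three factors, including whether one fentanyl factor is meant for all four listed routes. If they are mg-for-mg, revise Table 8 in one of two ways:

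- keep mcg and change the factors to 300 / 1000 = 0.3 (fentanyl, remifentanil), 75 / 1000 = 0.075 (buprenorphine IM) and 37.5 / 1000 = 0.0375 (buprenorphine SL); or
- change the unit to mg and state in 6.9.2 that doses recorded in mcg are divided by 1000 before the factor is applied.

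Add a programmed check that flags any single administration whose MED exceeds a prespecified plausibility limit. These are analysis conversions only and have no bearing on treatment.

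The cost is small: three table cells or one sentence, plus the check. The protocol gives no conversion factors, so its text need not change, and no new data are required.

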6.9.2.1 Time to First Postsurgical Use of Opioid Medication

Time to first postsurgical use of opioid rescue medication will be computed in hours as the date and time of the first opioid rescue medication minus the date and time of the end of surgery. If a subject is not administered an opioid rescue medication, the time to first administration will be censored at 72 hours after surgery or at the time of last follow-up, whichever is earliest. Time to first opioid consumption will be summarized by the quartiles (25th, 50th, and 75th), minimum and maximum estimated using Kaplan-Meier methods within age group and part of the study. The quartile and the 95% confidence limits (CONFTYPE=LOGLOG) for each quartile will be presented.

A Kaplan-Meier plot of the time from end of surgery to first opioid rescue medication use will be presented within age group and part of the study, and a log-rank test p-value of treatment difference shown for group 1.

6.10 Interim Analysis

Not Applicable.

6.10.1 Sample Size Review

The sample size was based on the number of subjects necessary to characterize the PK of EXPAREL in pediatric subjects with the precision required by the Food and Drug Administration.

6.11 Deviations from the Protocol

This SAP has an additional analysis that was not specified in the Protocol. Pharmacokinetic parameters will be calculated with a NCA method as specified in Section 6.7.2.

9. TIME AND EVENTS SCHEDULE OF STUDY PROCEDURES

	Screen Visit	D1 Preop	OR	15 min	30 min	1 h	2 h	4 h	8 h	12 h	24 h	36 h	48 h	60 h	72 h	96 h	Hosp Dis	D7 Call	D30 Visit
Time Window	Within 30 days			±5 min	±5 min		±15 min			±l h	±l h	±2 h	±2 h	±2 h	±2 h	±4 h		±l d	±3 d
Obtain signed informed consent/assent	X										Ι								
Assess/confirm eligibility	Х	Х	Х																
Record medical history and surgical history	Х	Х																	
Record demographics and baseline characteristics	Х																		
Urine pregnancy test (for females of childbearing potential; Part 1 only)	x	х																	
Urine drug screen and alcohol breath test at the investigator's discretion (Part 1 only).	x	x																	
Physical examination	Х																		Х
12-lead ECG ¹	X	2																	
Clinical laboratory tests (hematology, chemistry, urinalysis) ³	x	х														x			
Perform neurological assessment	х						Х	х	х	х	х	х	х	х	х	Х	х		х
Measure and record vital signs ⁴	Х	Х					Х	х	Х	Х	Х	Х	Х	Х	Х	Х	х		х
Record age-specific pain intensity score ⁵	Х							Х	Х	Х	Х	Х	Х	Х	Х	Х	Х		
Collect PK blood samples per time windows in Table 2				↓ -											- +				
Prepare study medication			х																
Administer study medication; record dosage, volume, size of incision, and administration start and stop times			х																
Record intraoperative opioids administered and doses			Х																
Record surgery start and stop times			Х																
Record times and doses of all pain management medication administered			+													•			
Record date and time of discharge																	х		

		Screen Visit	D1 Preop	OR	15 min	30 min	1 h	2 h	4 h	8 h	12 h	24 h	36 h	48 h	60 h	72 h	96 h	Hosp Dis	D7 Call	D30 Visit
	Time Window	Within 30 days			±5 min	±5 min	±15 min	±15 min	±15 min	±30 min	±l h	±l h	±2 h	±2 h	±2 h	±2 h	±4 h		±l d	±3 d
Document any unscheduled p office visits, or ER visits rela																			x	х
Record prior and concomitan	t medications ⁶	+																		► X
Record AEs beginning at the signed ^{1,3,4,7}	time the ICF or assent is	+																		► X

Note: Postsurgical assessments will be conducted at the time points specified after the end of study drug administration.

In the situation where PK blood draws and other assessments coincide or occur at about the same time, the blood draw for PK analysis must be conducted first, and the pain intensity assessment conducted second, as applicable, followed by any other assessments.

1 ECG abnormalities that are clinically significant should be recorded as AEs. May also conduct a 12-lead ECG if a subject experiences an AESI (i.e., cardiac AE or neurological AE), or an SAE; see footnote 7.

2 A baseline 12-lead ECG must be recorded prior to surgery and may be performed either at the screening visit or in the preoperative holding area on Day 1.

3 May also conduct clinical laboratory tests if a subject experiences an AESI or an SAE; see footnote 7.

4 Vital signs (temperature, resting heart rate, respiratory rate, oxygen saturation and blood pressure) will be measured after the subject has rested in a supine position for at least 5 minutes. May also measure vital signs if a subject experiences an AESI (i.e., cardiac AE or neurological AE), or an SAE; see footnote 7.

5 Pain intensity will be measured using the 11-point NRS-R for subjects aged 12 to less than 17 years (Appendix 1) and CAS for subjects aged 6 to less than 12 years (Appendix 2). The preoperative pain intensity assessment should be conducted immediately prior to each administration of postoperative opioid pain management medication till 96 hours. If a subject is too anesthetized at the time of a scheduled pain intensity assessment, the assessment should be skipped.

6 Instruct subject to discontinue prohibited medications. Record date/time of all medications starting at least 30 days prior to study drug administration till 96 hours after study drug administration. Record medications administered for treatment of an AE till Day 30.

7 In case a cardiac or neurological AE of special interest (AESI) or serious AE (SAE) occurs during the study, if the investigator or medical monitor considers that the event may be related to study treatment or suggests the possible occurrence of local anesthetic systemic toxicity (LAST; with or without the need for treatment [e.g., intralipids]), or if a plausible etiology for the event cannot be found, an unscheduled PK blood sample must be collected and a 12-lead ECG, vital signs, and clinical laboratory tests (hematology and complete metabolic profile [CMP]) according to the study site's standard of care may be conducted. See Section 13.1.7 and Appendix 6 for additional information on handling of AESIs. Cardiac or neurological events that do not meet one of these three criteria should be reported as described in Section 14.1.

Cardiac AESIs include chest pain, abnormal/irregular heart rate, and shortness of breath requiring intervention. Neurologic AESIs include seizure, altered mental status/altered sensorium, rigidity, dysarthria, tremors, tinnitus, visual disturbance, and severe or worsening dizziness. Additionally, the following events may be of special interest if they persist or occur beyond 72 hours post dose: dizziness, hyperesthesia, muscular twitching, and tingling/paresthesia. Severity of dizziness will be assessed based on NCI CTCAE (Version 5.0). Dizziness will be captured as an AESI if it is severe or worsens or persist beyond 72 hours post dose (see Section 13.1.7).

Abbreviations:

AE: adverse event; AESI: AE of special interest; CAS: Color Analog Scale; CTCAE: Common Terminology Criteria for Adverse Events; d: day(s); ECG: electrocardiogram; ER: emergency room; h: hour; Hosp Dis: hospital discharge; ICF: informed consent form; min: minutes; NCI: National Cancer Institute; NRS-R: Numeric Rating Scale at Rest; OR: operating room; PK: pharmacokinetic; SAE: serious adverse event.

